6.6 Dose Modifications for Toxicity

Adverse events (both non-serious and serious) associated with Pembrolizumab exposure may represent an immunologic etiology. These AEs may occur shortly after the first dose or several months after the last dose. Pembrolizumab must be withheld for drug-related toxicities and severe or life-threatening AEs as per Table 8 below. See Section 6.8 for supportive care guidelines, including use of corticosteroids.

Treatment discontinuation for AST, ALT deterioration in participants who present with Grade 2 AST or ALT will be triggered only if AST or ALT increases by greater than or equal to 50% relative to the measurement taken at initiation of systemic treatment (Cycle 1 Day 1) and lasts for at least 1 week.

Toxicity	Hold Treatment For Grade	Timing for Restarting Treatment	Treatment Discontinuation
Diarrhoea/ Colitis	2-3	Toxicity resolves to Grade 0-1	Toxicity does not resolve within 12 weeks of last dose or inability to reduce corticosteroid to 10 mg or less of prednisone or equivalent per day within 12 weeks
	4	Permanently discontinue	Permanently discontinue
AST, ALT, or Increased Bilirubin	2	Toxicity resolves to Grade 0-1	Toxicity does not resolve within 12 weeks of last dose
	3-4	Permanently discontinue (see exception below) ^a	Permanently discontinue
Type 1 diabetes mellitus (if new onset) or Hyperglycaemia	T1DM or 3-4	Hold Pembrolizumab for new onset Type 1 diabetes mellitus or Grade 3-4 hyperglycemia associated with evidence of beta cell failure	Resume Pembrolizumab when participants are clinically and metabolically stable
Hypophysitis	2-4	Toxicity resolves to Grade 0-1. Therapy with Pembrolizumab can be continued while endocrine replacement therapy is instituted	Toxicity does not resolve within 12 weeks of last dose or inability to reduce corticosteroid to 10 mg or less of prednisone or equivalent per day within 12 weeks
Hyperthyroidism	3	Toxicity resolves to Grade 0-1	Toxicity does not resolve within 12 weeks of last dose or inability to reduce corticosteroid to 10 mg or less of prednisone or equivalent per day within 12 weeks
	4	Permanently discontinue	Permanently discontinue
Hypothyroidism		Therapy with Pembrolizumab can be continued while thyroid replacement therapy is instituted	Therapy with Pembrolizumab can be continued while thyroid replacement therapy is instituted

Toxicity	Hold Treatment For Grade	Timing for Restarting Treatment	Treatment Discontinuation

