Infusion Reaction	2 ^b	Toxicity resolves to Grade 0-1	Permanently discontinue if toxicity develops despite adequate premedication
	3-4	Permanently discontinue	Permanently discontinue
Pneumonitis	2	Toxicity resolves to Grade 0-1	Toxicity does not resolve within 12 weeks of last dose or inability to reduce corticosteroid to 10 mg or less of prednisone or equivalent per day within 12 weeks
	3-4	Permanently discontinue	Permanently discontinue
Renal Failure or Nephritis	2	Toxicity resolves to Grade 0-1	Toxicity does not resolve within 12 weeks of last dose or inability to reduce corticosteroid to 10 mg or less of prednisone or equivalent per day within 12 weeks
	3-4	Permanently discontinue	Permanently discontinue
All Other Drug-Related Toxicity ^c	3 or Severe	Toxicity resolves to Grade 0-1	Toxicity does not resolve within 12 weeks of last dose or inability to reduce corticosteroid to 10 mg or less of prednisone or equivalent per day within 12 weeks
	4	Permanently discontinue	Permanently discontinue

Note: Permanently discontinue for any severe or Grade 3 drug-related AE that recurs or any life-threatening event.

^a For participants who begin treatment with Grade 2 AST or ALT at Cycle 1 Day 1 of treatment, if AST or ALT increases by greater than or equal to 50% relative to baseline and lasts for at least 1 week then participants should be discontinued.

^b If symptoms resolve within one hour of stopping IMP infusion, the infusion may be restarted at 50% of the original infusion rate (e.g., from 100 mL/hr to 50 mL/hr). Otherwise dosing will be held until symptoms resolve and the participant should be pre-medicated for the next scheduled dose.

^c Participants with intolerable or persistent Grade 2 drug-related AE may hold study medication at PI/delegate discretion. Permanently discontinue IMP for persistent Grade 2 adverse reactions for which treatment with IMP has been held, that do not recover to Grade 0-1 within 12 weeks of the last dose.

Table 8: Dose Modification Guidelines for Drug-Related Adverse Events

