6.8.2 Supportive Care Guidelines for Immune-related Adverse Event (irAE) and Immune-related Events of Clinical Interest (irECI).

Immune-related Adverse events (IrAEs) may be defined as an AE of unknown etiology, associated with IMP exposure and is consistent with an immune phenomenon. IrAEs may be predicted based on the nature of the Pembrolizumab compound, its mechanism of action, and reported experience with immunotherapies that have a similar mechanism of action. Special attention should be paid to AEs that may be suggestive of potential irAEs. An irAE can occur shortly after the first dose or several months after the last dose of IMP.

If an irAE is suspected, efforts should be made to rule out neoplastic, infectious, metabolic, toxin or other etiologic causes prior to labelling an AE as an irAE. Participants who develop a Grade 2 or higher irAE should be discussed immediately with the CI/designee.

Recommendations to managing irAEs not detailed elsewhere in the protocol are detailed in Table 10.

irAE	Withhold/Discontinue Pembrolizumab?	Supportive Care
Grade 1	No action	Provide symptomatic treatment
Grade 2	May withhold Pembrolizumab	Consider systemic corticosteroids in addition to appropriate symptomatic treatment. Steroid taper should be considered once symptoms improve to Grade 1 or less and tapered over at least 4 weeks.
Grade 3 and Grade 4	Withhold Pembrolizumab Discontinue if unable to reduce corticosteroid dose to < 10 mg per day prednisone equivalent within 12 weeks of toxicity	Systemic corticosteroids are indicated in addition to appropriate symptomatic treatment. May utilize 1 to 2 mg/kg prednisone or equivalent per day. Steroid taper should be considered once symptoms improve to Grade 1 or less and tapered over at least 4 weeks.

Table 10: General Approach for Handling irAEs

Details for managing specific irAEs are summarised below:

Immune-mediated pneumonitis

Monitor participants for signs and symptoms of pneumonitis. If pneumonitis is suspected, evaluate with radiographic imaging. Exclude other causes of pneumonitis, and manage treatment in accordance with the

guidelines above. Administer corticosteroids, withhold Pembrolizumab for moderate (Grade 2) pneumonitis, and permanently discontinue Pembrolizumab for severe (Grade 3) or life-threatening (Grade 4) pneumonitis.

Immune-mediated colitis

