7.2.1.1 Determining AE Severity and Grade

AE severity and grade will be evaluated according to the NCI CTCAE version 4.0. Any AE which changes CTCAE grade over the course of a given episode should be closed at the date and time the severity changed and a new AE recorded from the date and time of the new NCI CTCAE grade.

Grade 1	Mild; asymptomatic or mild symptoms; clinical or diagnostic observations only; intervention not indicated.
Grade 2	Moderate; minimal, local or non-invasive intervention indicated; limiting age-appropriate instrumental ADL.
Grade 3	Severe or medically significant but not immediately life-threatening; hospitalisation or prolongation of hospitalisation indicated; disabling; limiting self-care ADL.
Grade 4	Life threatening consequences; urgent intervention indicated.
Grade 5	Death related to AE

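### Table 10 gives no permanent stop for a Grade 4 non-endocrine irAE that lacks its own Table 8 row; Table 8 requires one, and no text says which table governs

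*Combined protocol and SAP*

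**What the plan says.** **Table 8 (Section 6.6).** The section introduces the table in mandatory terms: "Pembrolizumab must be withheld for drug-related toxicities and severe or life-threatening AEs as per Table 8 below". Nine rows cover named toxicities. A tenth, "All Other Drug-Related Toxicity", covers the rest: at Grade 3 or severe, hold and restart on recovery to Grade 0-1; at Grade 4, permanently discontinue. Below the table stands: "Note: Permanently discontinue for any severe or Grade 3 drug-related AE that recurs or any life-threatening event". Section 7.2.1.1 defines Grade 4 as "Life threatening consequences; urgent intervention indicated", so the note reaches every Grade 4 event.

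**Table 10 (Section 6.8.2).** Its scope is given as: "Recommendations to managing irAEs not detailed elsewhere in the protocol are detailed in Table 10". It has its own column on withholding and discontinuing pembrolizumab. Grades 3 and 4 share one row: withhold, then "Discontinue if unable to reduce corticosteroid dose to < 10 mg per day prednisone equivalent within 12 weeks of toxicity". There is no separate Grade 4 line and no restart column.

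**Pointers between them.** Section 6.8.1 refers the reader to Section 6.6 for dose modification. Section 6.8.1.8 sends events of possible immunologic cause to Section 6.8.2. Section 6.8.2 requires an immediate stop for symptomatic immune-related events of clinical interest (irECIs), then sends those judged associated with the drug to Section 6.8.3, which is hepatic guidance. It also says: "Participants who develop a Grade 2 or higher irAE should be discussed immediately with the CI/designee".

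**The concern.** Section 6.8.2 defines an irAE as an "AE of unknown etiology, associated with IMP exposure and is consistent with an immune phenomenon". An event attributed to the drug in this way is also a drug-related toxicity, so one without its own Table 8 row falls under both Table 10 and Table 8's catch-all row. At Grade 4 the two do not give the same instruction. Table 8 ends treatment. Table 10 withholds it and names a failed steroid taper as the only reason to end it.

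A site that opens Section 6.8.2 to manage a Grade 4 myocarditis could take a successful taper as clearing the way to re-dose. Section 1.2.2 reports one fatal myocarditis and one fatal SJS case in clinical trials, so an unintended rechallenge would be serious even if very unlikely. What is at stake is participant safety and consistent conduct across sites, not the analysis.

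**Working it through.** No sample-size or power figure is involved. The check is a comparison of instructions, followed by a bound on frequency.

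**1. Which events fall under both tables.** Table 8's named rows are diarrhoea/colitis, AST/ALT/bilirubin, type 1 diabetes/hyperglycaemia, hypophysitis, hyperthyroidism, hypothyroidism, infusion reaction, pneumonitis and renal failure/nephritis. Myocarditis, pancreatitis, uveitis, SJS and TEN are not among them. All five are listed as irECIs in Table 12 (Section 7.4).

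**2. Instruction for a Grade 4 event of this kind.**

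| Source | Instruction |
|---|---|
| Table 8, catch-all row | Permanently discontinue |
| Table 8, note | Permanently discontinue (life-threatening) |
| Table 10, Grade 3 and 4 row | Withhold; discontinue if the steroid taper fails within 12 weeks |
| Section 6.8.2, symptomatic irECI | Stop at once; not stated to be permanent |
| Section 6.8.3, where 6.8.2 sends associated irECIs | Hepatic events only |

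**3. What Section 6.8.2 says on its own.** After Table 10 it restates a permanent Grade 4 stop for pneumonitis, colitis, nephritis and hyperthyroidism. It gives none for uveitis, severe skin reactions, myocarditis or pancreatitis.

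**4. Pattern in Table 8.** Seven of its 10 rows stop permanently at Grade 4: colitis, AST/ALT/bilirubin (with a stated exception for raised baseline AST or ALT), hyperthyroidism, infusion reaction, pneumonitis, renal, and the catch-all. That includes all 6 non-endocrine rows. The 3 rows without such a stop are endocrine: diabetes/hyperglycaemia, hypophysitis and hypothyroidism.

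**5. Frequency.** The documents give no Grade 4 counts, so only a bound is possible, and only for the two event types with trial counts.

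- Inputs (Section 1.2.2): about 11,000 clinical-trial patients; 6 myocarditis cases, 1 fatal; 6 clinical-trial SJS cases, 1 fatal. Both TEN cases were post-marketing and are not counted.
- Non-fatal cases: (6 − 1) + (6 − 1) = 10.
- Rate: 10 / 11,000 = 0.000909 per patient.
- Expected in 32 participants (Section 3.1): 32 × 0.000909 = 0.029.
- Chance of at least one: 1 − (1 − 0.000909)^32 = 0.0287, or 2.9%, if every case were Grade 4.
- If half were Grade 4 (assumption): 5 / 11,000 gives 1 − (1 − 0.000455)^32 = 0.0144, or 1.4%.
- If a tenth were Grade 4 (assumption): 1 / 11,000 gives 1 − (1 − 0.0000909)^32 = 0.0029, or 0.3%.

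Pancreatitis has no count, and uveitis and severe skin reactions are given only as under 1% across all grades, so uveitis and pancreatitis are left out.

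**The case against.** The strongest reply is that both tables can be obeyed. Table 10 lists one sufficient reason to discontinue; it does not say that this is the only permitted reason, and it grants no restart. A site that stops permanently under Table 8 breaches nothing in Table 10. This stands. A reader might infer that Table 10 authorises rechallenge after a Grade 4 event; the documents do not say that.

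It is also fair that the text leans towards Table 8. Section 6.6 is mandatory, Section 6.8.1 points to it for dose modification, and Table 10 offers recommendations for irAEs not covered elsewhere. But if the catch-all row counts as coverage elsewhere, Table 10's Grade 4 dosing instruction has almost nothing left to govern, although its steroid and taper advice would still apply. The leaning is strong, but it is not a stated rule.

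A reader might also infer that the merged row is out of line with the whole protocol. That goes too far. It departs from Table 8's non-endocrine rows, but Section 6.8.3 itself allows interruption and possible restart for some hepatic events, including immune-related hepatitis once it has resolved and steroids are tapered.

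Finally, there are safeguards: immediate discussion of Grade 2 or higher irAEs with the CI or designee, the immediate stop for symptomatic irECIs, and discontinuation for unacceptable AEs in Section 6.11.1 (a term left undefined). They reduce the risk. They do not put the permanent stop where the site is sent to look.

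**Conclusion.** The inconsistency holds in a limited form. For a Grade 4 non-endocrine irAE without its own Table 8 row, Table 8 requires a permanent stop, while Table 10 says withhold and leaves restart implied but unstated. Table 8 most likely governs, but no sentence says so, and the pointers in Sections 6.8.1.8 and 6.8.2 lead away from it. This is a low-frequency participant-safety correction, worth making because it is so cheap.

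The 2.9% bounds the chance of at least one non-fatal myocarditis or SJS case. A reader might take it as the chance of an unsafe restart, and it is not: a restart would also need recovery, a taper within 12 weeks, and a decision contrary to Table 8 after discussion with the CI. The bound assumes that the background rate carries over. Two features bear on that. The myocarditis count includes an expanded access program of unstated size, which the 11,000 may not cover. And Section 1.2.2 lists anthracycline as a myocarditis risk factor while TACE here uses doxorubicin, an effect that the documents do not quantify.

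Nor does the point reach the primary analysis. Events are counted and graded in the same way whichever table a site follows.

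**What to change.** Split only the last row of Table 10 and leave the supportive-care column as it is.

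- **Grade 3:** keep the present text and add *see also Table 8*.
- **Grade 4:** *Permanently discontinue (see Table 8); for endocrinopathies follow their specific text in Table 8 and Section 6.8.2.*

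Do not add a general precedence sentence. Section 6.8.2 lets continuation be considered after a Grade 4 endocrinopathy controlled with hormone replacement, while Table 8 and the same section permanently stop Grade 4 hyperthyroidism. A precedence rule with an endocrine exception could relax that stop, which is a separate clinical decision.

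Do not rewrite the Grade 3 rule here either. Table 8 counts its 12 weeks for non-resolution from the last dose and Table 10 counts from the toxicity, the steroid thresholds differ slightly (10 mg or less against below 10 mg), and Table 8's note adds a permanent stop for recurrent Grade 3 events. The pointer to Table 8 keeps that note in view.

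The cost is one table row. The downside is that a rare participant who recovers from such a Grade 4 event cannot restart, which Table 8 already requires. Sample size, endpoints and analyses do not change.

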- If laboratory abnormalities do not resolve within 3 weeks, or steroids cannot be lowered to ≤ 10 mg/day (or prednisone equivalent) within 12 weeks, or participants show evidence of decompensation to Child-Pugh C status or have esophageal or variceal bleeding at any point, treatment must be permanently discontinued. This must be documented.

d. Other Hepatic Events of Clinical Interest

- Infection needs to be ruled out with cultures of blood, urine, and ascites (if possible), as well as chest x-ray and abdominal imaging if relevant. If an infection is found, antibiotics should be started.
- If Tbil is elevated above baseline, magnetic resonance cholangiopancreatography or ultrasound with doppler should be obtained to rule out vascular compromise, biliary obstruction, and/or tumour progression. If biliary obstruction is present, consultation with a gastroenterologist and/or an interventional radiologist should be obtained to see if the obstruction may be relieved.
- A careful review of drugs, including herbal and alternative medications, should be obtained, and alcohol use should be ruled out.

- For all of these cases, participants may resume Pembrolizumab treatment if they are clinically stable after appropriate therapy or discontinue the causative agent, as long as laboratory values have returned to Grade 1 or baseline (if normal or Grade 1 at start) or to baseline grade within 3 weeks.
- Treatment must be permanently discontinued if the participant is off Pembrolizumab therapy for infection, obstruction, or drug/alcohol-related toxicity for more than 3 weeks, or if they have oesophageal bleeding, or become Child-Pugh C at any point.

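### Grade 3 immune-related events without their own row in Table 8: Tables 8 and 10 give opposite stopping instructions at exactly 10 mg/day of prednisone

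*Combined protocol and SAP*

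**What the plan says.** **Section 6.6, Table 8.** The lead-in makes the table binding: "Pembrolizumab must be withheld for drug-related toxicities and severe or life-threatening AEs as per Table 8 below". Toxicities without their own row fall in the row "All Other Drug-Related Toxicity". At Grade 3 or severe, that row holds treatment until the event returns to Grade 0-1. It discontinues on either of two conditions:
- "Toxicity does not resolve within 12 weeks of last dose"
- "inability to reduce corticosteroid to 10 mg or less of prednisone or equivalent per day within 12 weeks"

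The resolution condition is timed from the last dose. The steroid condition has no stated start date.

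**Section 6.8.2, Table 10.** Its scope is residual: "Recommendations to managing irAEs not detailed elsewhere in the protocol are detailed in Table 10". It has its own column on whether to withhold or stop pembrolizumab. For Grades 3 and 4 together it withholds, then says: "Discontinue if unable to reduce corticosteroid dose to < 10 mg per day prednisone equivalent within 12 weeks of toxicity". It sets no deadline for resolution of the event.

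**Section 6.8.3, immune-related hepatitis.** Treatment stops if "steroids cannot be lowered to ≤ 10 mg/day (or prednisone equivalent) within 12 weeks", and may restart once the steroid is down to 10 mg/day or less. This is the same inequality as in Table 8.

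**The concern.** Some Grade 3 immune-related events meet the scope of both tables, and the tables put the boundary dose on opposite sides. At 10 mg/day Table 8 is satisfied and Table 10 is not. The consequence is permanent discontinuation, so the difference decides whether a participant may resume study drug.

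It also reaches the results. Safety and tolerability is the primary endpoint, and section 8.3 summarises adverse events by, among other things, their effect on study drug. If sites apply different tables, that summary partly reflects which table was used and not only how the treatment was tolerated.

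**Working it through.** The plan gives no figure to reproduce. The check applies both rules to one event.

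**Test event.** Grade 3 drug-related uveitis. Section 6.8.2 and Table 12 both name uveitis as immune-related. It has no row in Table 8 and no management paragraph of its own. Table 8's catch-all row therefore covers it as a drug-related toxicity, and Table 10 covers it as an immune-related event without specific guidance. Colitis, pneumonitis, hepatitis, nephritis, hypophysitis, thyroid disorders and diabetes have their own text, so Table 10's scope line removes them from the overlap.

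**Steroid threshold.** Let d be the daily prednisone-equivalent dose at the 12-week limit. Assume the event has returned to Grade 0-1 in time, so that Table 8's resolution condition is met.

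| d (mg/day) | Table 8: stop if d > 10 | Table 10: stop if d ≥ 10 |
|---|---|---|
| below 10 | not stopped | not stopped |
| exactly 10 | not stopped | permanently stopped |
| above 10 | permanently stopped | permanently stopped |

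The tables disagree at one value only. That value is not arbitrary: it is the highest steroid dose at which 6.8.3 allows restart after immune-related hepatitis. A taper aimed at the same target for another event would land on it.

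**Time limits.** Put the last dose at day 0 and onset at day t. Twelve weeks is 12 × 7 = 84 days.
- Table 8, resolution: day 84.
- Table 8, steroid: 84 days from an unstated start.
- Table 10, steroid: day 84 + t.
- Table 10, resolution: none.

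The two dated limits, day 84 and day 84 + t, bound different things: resolution in one table, steroid dose in the other. If Table 8's steroid condition were read as running from the last dose, the steroid deadlines would differ by t. If it were read as running from onset, they would coincide. The documents do not say which.

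The missing resolution limit in Table 10 is a further difference. If the event is unresolved at day 84 but the steroid is already below 10 mg/day, Table 8 stops treatment and Table 10 has no trigger. This should be uncommon, because Table 10 starts the taper only after improvement to Grade 1 or less. Table 10's silence is also not an instruction to continue.

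**Size.** Section 6.8.2 reports uveitis and severe skin reactions in fewer than 1% of about 5000 participants treated elsewhere. If that rate carried over and applied to each, 32 participants would give fewer than 0.01 × 32 = 0.32 cases of each, before requiring Grade 3 and a dose of exactly 10 mg/day. Other events in the overlap would add to this, at rates the documents do not give. One discontinuation decided by the choice of table is 1/32 = 3.1% or 1/26 = 3.8% of evaluable participants.

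**The case against.** **Table 8 already leads.** Section 6.6 makes Table 8 mandatory and sends the reader to 6.8 for supportive care. Section 6.8.1 describes its measures as suggestions and points back to 6.6 for dose changes. Table 10 is limited to events not covered elsewhere. A reader who infers that the plan is silent on precedence goes too far, because these passages favour Table 8. They still do not settle it. The pointer back to 6.6 sits in a note on events judged unrelated to pembrolizumab, and Table 10 has its own column on withholding and stopping. If the catch-all row counted as coverage elsewhere, Table 10 would have little or no use for Grade 3-4 drug-related events.

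**The clocks do not conflict.** A reader might infer that the two steroid deadlines differ by about three weeks, because a 21-day cycle with a ± 3-day window lets onset fall up to about 24 days after the last dose. The documents do not support this. The last-dose clock in Table 8 limits resolution, not steroid reduction, and its steroid condition has no start date. The bound also needs onset before the next dose, while 6.8.2 allows onset months after the last one. This objection stands in full. What remains is an undefined start date.

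**There is a central check.** Events of Grade 2 or higher are to be discussed immediately with the chief investigator or designee, so a site should not decide alone. This reduces inconsistency between sites. However, the chief investigator works from the same two tables.

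**The reach is small and the analysis descriptive.** Both are true. No test, power figure or error rate is affected. This sets the severity but does not remove the contradiction.

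**Conclusion.** The contradiction is real but narrow. For a Grade 3 drug-related immune-related event without its own row in Table 8, resolved in time and with steroid at exactly 10 mg/day at the 12-week limit, Table 8 does not discontinue and Table 10 discontinues permanently. Separately, only Table 10 dates the start of the steroid limit, and only Table 8 sets a resolution deadline.

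The conclusion rests on two readings: that the catch-all row covers immune-related events judged drug-related, and that no text makes either table override the other. It does not extend to immune-related events in general, nor to any stated gap between steroid deadlines.

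Severity is minor. The expected number of affected participants is small, and the consequence is limited to individual treatment decisions and the descriptive tolerability summary.

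The same rows hold a separate conflict at Grade 4. Table 8 discontinues permanently, and its note adds "Permanently discontinue for any severe or Grade 3 drug-related AE that recurs or any life-threatening event", whereas Table 10 withholds and stops only if the taper fails. The two points are best handled together.

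**What to change.** Reconcile Tables 8 and 10 so that they share one inequality and one stated start date for the 12-week steroid limit. Say whether Table 8's resolution deadline also applies to events managed under Table 10. Add one sentence stating which table governs when both apply. Check 6.8.3 against the result: its inequality matches Table 8 now, but its 12-week limit also lacks a start date. Resolve the Grade 4 conflict in the same edit. Which limit and which start date are right is a clinical decision for the sponsor.

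The cost is wording in two tables, one sentence on precedence and a consistency check of 6.8.3, made through the amendment route in 9.3.2. Sample size, visit schedule and analysis methods do not change.
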